NA	Not Applicable
QC	Quality Control
RA	Rheumatoid Arthritis
SAE	Serious Adverse Event
SBP	Systolic Blood Pressure
SD	Standard Deviation

Study Protocol: EVA_CLEAR_11022017

SDAI	Simple Disease Activity Index
SOP	Standard Operating Procedure
Sr ACPA	Serum Anti-Citrullinated Peptide Antibody
Sr RF	Serum Rheumatoid Factor
Sr Cr	Serum Creatinine
WHO	World Health Organization

3. Synopsis

STUDY TITLE	A Phase IV, Multi-Centric, Prospective, Observational Study to Assess the C linical Efficacy and Safety of L eflunomide in Egyptian Patients with A ctive R heumatoid Arthritis. (CLEAR)		
STUDY CODE	EVA_CLEAR_11022017		
STUDY SPONSOR	EVAPHARMA Egypt		
PRODUCT NAME	Arthfree		
ACTIVE INGREDIENT	Leflunomide		
INDICATION	Active Rheumatoid Arthritis		
STUDY LOCATION (S)	Egypt		
	[name] (Professor of Internal Medicine, Rheumatology and Immunology)		
PRINCIPLE INVESTIGATOR	Head of Rheumatology Department, Faculty of Medicine, Ain Shams University, Abbasiya, Cairo, Egypt.		
	Address: [name]		
	[contact]		
	Email: [name] [contact]		
SPONSOR'S MEDICAL EXPERT	[name] Address: [name] Mobile: [name] Email: [contact]		
CENTRAL LABORATORY	NA		
MEDICAL AND/OR TECHNICAL DEPARTMENTS	NA		
STUDY QUESTIONS	 What is the clinical efficacy of Leflunomide as first line therapy and as add-on therapy to other DMARDs (such as Methotrexate, Hydroxychloroquine, and Sulfasalazine) with or without Steroids use in Egyptian patients with Active Rheumatoid Arthritis? What are the pattern of management and characteristics of Egyptian patients with Active Rheumatoid Arthritis receiving Leflunomide treatment? What is the clinical safety of Leflunomide as first line therapy and 		

	as add-on therapy to other DMARDs (such as Methotrexate, Hydroxychloroquine, and Sulfasalazine) with or without Steroids use in Egyptian patients with Active Rheumatoid Arthritis?			
	 Primary Objective: 1. Assessing the clinical efficacy of Leflunomide as first line therapy and as add-on therapy to other DMARDs (such as Methotrexate, Hydroxychloroquine, Sulfasalazine) with or without Steroids in Egyptian patients with Active Rheumatoid Arthritis. 			
STUDY OBJECTIVES	 Secondary Objectives: Describing pattern of management and characteristics of Egyptian patients with Active Rheumatoid Arthritis receiving Leflunomide treatment. Identifying the safety profile of Leflunomide whether used as first line therapy and/or as add-on therapy to other DMARDs (such as Methotrexate, Hydroxychloroquine, Sulfasalazine) with or without Steroids in Egyptian patients with Active Rheumatoid Arthritis. 			
	Study Design Description: This is a phase IV, multi-centric, prospective, observational study to assess the clinical efficacy and safety of Leflunomide as first line therapy and as add-on therapy to other DMARDs (such as Methotrexate, Hydroxychloroquine, Sulfasalazine) with or without Steroids use in Egyptian patients with Active Rheumatoid Arthritis.			
	3 months for recruitment and 9 months for treatment. Sample Size:			
SUMMARY OF STUDY DESIGN	It is estimated to recruit 400 patients (around 17 patients per site). Patients will be between 18 and 60 years of age, with Active Rheumatoid Arthritis selected according to the ACR/EULAR classification criteria with score \geq 6 points.			
	Patients will be Leflunomide naïve or after previous Leflunomide administration (after at least 6 month wash out period from date of baseline visit).			
	Patients will be with or without other DMARDs including Methotrexate, Sulfasalazine and/or Hydroxychloroquine with or without steroids use who experienced therapy resistance, inadequate response or intolerance.			

	Selection of Patients:				
	Inclusion Criteria:				
	Patient must meet ALL of the following criteria to be eligible for enrolment into the study				
RECRUITMENT MODALITIES	 Active Rheumatoid Arthritis patients selected according to the ACR/EULAR classification 2010 criteria with score ≥ 6 points. Male or female patients aged 18-60 years old. Leflunomide naïve patients or patients with previous Leflunomide administration (after at least 6 month wash out period from date of baseline visit) who will be prescribed Leflunomide at the sole decision of the treating physician. Patients with or without another DMARDs including Methotrexate, Sulfasalazine and/or Hydroxychloroquine with or without steroids use who experienced therapy resistance, inadequate response or intolerance. Patients read, understand and signed informed consent prior to inclusion. Patients willing to complete and literate in the language of the available Health Assessment Questionnaire (HAQ Disability Index) either alone or with minimal assistance from caregivers and/or trained site personnel. 				
	Exclusion Criteria:				
	Patient meeting the following criteria is not eligible for enrolment into the study				
	 Female patients who are pregnant or lactating at the time of inclusion or those who are planning for pregnancy within the coming year from the time of inclusion to the study. Patients with contraindications to active constituent of Leflunomide. Patients with severe concurrent infection (necessitating IV antibiotics or hospitalization). Patients with history of non-treated hepatitis B &/or C infection. Patients with history of severe liver disease (child C class). 				
	 Patients with history of severe renal insufficiency (creatinine clearance ≤30 ml/min.). 				
	Selection of Investigators:				
	The study will be conducted by rheumatologists.				
	In order to ensure the representativeness of investigators, the participating investigators will be randomly selected among an extended list of sites (private clinics; rheumatologist) provided by the				

	study sponsor.					
TOTAL EXPECTED NUMBER OF PATIENTS	It is estimated to recruit around 17 patients per site (Total 400 patients).					
EXPECTED NUMBER OF SITES	24 sites (Private clinics)					
MEDICINAL PRODUCT	Arthfree (Leflunomide 20mg) Dose: 1 tablet once daily, should be swallowed whole with sufficient amounts of liquids. The extent of Leflunomide absorption is not affected if taken with meals. Doses higher than 20 mg/day are not recommended. Improvement in the rheumatoid condition usually starts after 4 to 6 weeks and may further improve up to 4 to 6 months. Loading dose: a tablet of Leflunomide 100 mg for three days. should be swallowed whole with sufficient amounts of liquids. The extent of Leflunomide absorption is not affected if taken with meals. Due to the long half-life in patients with rheumatoid arthritis and recommended dosing interval (24 hours), a loading dose is needed to provide steady-state concentrations more rapidly. Patients will be prescribed Arthfree (Leflunomide) at the sole decision of the treating physician.					
	This phase IV study will last for 9 months in addition to recruitment period of 3 months. A total of 6 visits will be performed as shown in the table below;					
	Visit 1	Visit 2	Visit 3	Visit 4	Visit 5	Visit 6
DATA COLLECTION SCHEDULE	Baseline & ICF signing	Week 6 (± 2 weeks)	Week 12 (± 2 weeks)	Week 20 (± 2 weeks)	Week 28 (± 2 weeks)	Week 36 (± 2 weeks) EOS
	Clinical Assessment	Clinical Assessment	Clinical Assessment if applicable Clinica Assessm		Clinical Assessment	
	Lab Data	Lab Data Lab Data if applicable Lab		Lab Data		
	Safety Data					
DATA TO BE COLLECTED (FOR PRIMARY AND SECONDARY OBJECTIVES)**	 At Baseline Visit: Data on Informed consent, Inclusion and exclusion criteria, Demographics, Smoking status, Alcohol consumption, Medical history, Gynecological History for female patients only, Concomitant medications, Laboratory tests and Poor prognostic factors will be 					

	collected along with RA history.				
	Disease assessment (CDAI) and Physical examination will be done and also Vital signs will be recorded.				
	Patients will fill Health Assessment Questionnaire (HAQ Disability				
	Index) and related data will be recorded.				
	At Visit 2 (Week 6 ± 2 weeks) & Visit 3 (Week 12 ± 2 weeks) & Visit				
	4 (Week 20 ± 2 weeks) & Visit 5 (Week 28 ± 2 weeks):				
	Data on Concomitant medications and Laboratory tests will be collected.				
	Disease assessment (CDAI) and Physical examination will be done and also Vital signs will be recorded.				
	Patients will fill Health Assessment Questionnaire (HAQ Disability Index) and related data will be recorded.				
	Data on Adverse events/Serious adverse events experienced by patient since the previous visit will be documented.				
	At Visit 6 (Week 36 ± 2 weeks):				
	Data on Concomitant medications and Laboratory tests will be collected.				
	Disease assessment (CDAI) and Physical examination will be done and also Vital signs will be recorded.				
	Patients will fill Health Assessment Questionnaire (HAQ Disability Index) and related data will be recorded.				
	Data on Adverse events/Serious adverse events experienced by patient since the previous visit will be documented.				
	Study Completion Form will be also filled.				
	Primary Endpoints:				
STUDY ENDPOINTS	 To assess disease severity (Remission, Low activity, Moderate activity and High activity) and the mean relative change of in Clinical Disease Activity Index (CDAI) among patients with active rheumatoid arthritis treated with Leflunomide as first line therapy and as add-on therapy to other DMARDs (such as Methotrexate, Hydroxychloroquine, Sulfasalazine) with or without Steroids between baseline and week 36. 				
	- To assess the mean relative change in Health Assessment				
	Questionnaire score (HAQ Disability Index) among patients				

	with active rheumatoid arthritis treated with Leflunomide as						
	(such as Methotrexate, Hydroxychloroquine, Sulfasalazine)						
	with or without Steroids between baseline and week 36.						
	Secondary Endpoints:						
	 To describe pattern of management and patients' characteristics (including demographics, medical history, RA severity, RA Duration, line of therapy, daily dose, treatment duration, reasons for treatment adjustment and Previous therapies) of active RA patients receiving Leflunomide treatment. To assess the frequency of AEs/SAEs among patients using Leflunomide as first line therapy and as add-on therapy to other DMARDs (such as Methotrexate, Hydroxychloroquine, Sulfasalazine) with or without Steroids and its relation to study medication. 						
	Statistical Power and Sample Size Justification						
STATISTICAL CONSIDERATIONS	 The primary objective of CLEAR study is to assess the clinical efficacy of Leflunomide as first line therapy and as add-on therapy to other DMARDs (such as Methotrexate, Hydroxychloroquine, Sulfasalazine) with or without Steroids as measured by the mean relative change in Clinical Disease Activity Index (CDAI) and Health Assessment Questionnaire (HAQ Disability Index) among patients with active rheumatoid arthritis. Considering an alpha error of 5% using two-sided 95% CI of Wilcoxon signed-rank test and a study power of 80%, a sample of 332 patients will be required to detect an effect size of 0.158 between baseline and study endpoint, plus an expected drop-out rate of 20% during the 9 months observational study duration. Thus, a sample of 398 patients will be appropriate that rounded to 400 patients. Randomization method 						
	Not applicable.						
	Statistical methodologies:						
	- Descriptive analysis:						
	 Percent (%) distribution for all categorical variables and 						

	mean with (SD) and median (Minimum: Maximum) for				
	- Comparative analysis:				
	 Student t-test and One Way ANOVA to estimate the comparison between the treatment arms for the numerical variables (according to their distribution; non-parametric substitution tests could be used). 				
	 Paired t-test and repeated measure ANOVA test to estimate the change in numerical variables throughout the study visits (according to their distribution; non-parametric substitution tests could be used). Chi2 test (or Fisher's Exact test) for unpaired and McNemar's test for paired categorical variables. 				
	All tests will be performed on the 5% level of significance.				
	 Any deviation(s) from the original statistical plan will be described in the final report). 				
	 Procedure for accounting for missing, unused, and spurious data will be explained in the statistical analysis plan (SAP). 				
	Interim analysis				
	When approximately the enrolled patients completed 50% of their visits (after Visit 3), an interim analysis for safety and efficacy will be conducted by an independent data monitoring committee. Serious adverse events will be monitored by the committee on an ongoing basis throughout the study.				
	- Protocol planned date: June 2017				
	- First patient In (FPI): September 2017				
	- Last patient In (LPI): December 2017				
ESTIMATED DURATION	- Last patient Out (LPO): September 2018				
LOTIMATED DONATION	- Estimated enrollment duration: 3 months				
	- Estimate treatment duration: 9 months				
	- Database lock planned date: September 2018				
	 Estimated Report date: November 2018 				

	**Data Collection Schedule						
Data to be collected	Visit 1 (Baseline)	Visit 2 (Week 6)	Visit 3 (Week 12)	Visit 4 (Week 20)	Visit 5 (Week 28)	Visit 6 (Week 36)	
Informed consent	Х						
Inclusion/ Exclusion	Х						
Physical Examination/ Vital Signs ¹	Х	х	х	х	х	х	
Demographics	Х						
Smoking Status	Х						
Alcohol Consumption	Х						
Medical history	Х						
Gynecological History (FEMALES ONLY)	Х						
Concomitant	v	v	v	v	×	v	
Medications	X	X	X	X	X	X	
RA History ²	Х						
Disease Assessment ³	Х	Х	Х	Х	х	Х	
Laboratory Tests ⁴	Х	Х	Х	Х	х	Х	
Health Assessment Questionnaire (HAQ Disability Index)⁵	х	х	х	x	x	х	
Poor Prognostic Factors ⁶	х						
Adverse Events & Serious Adverse Events		х	х	х	Х	Х	
Study Completion Form						Х	
 Physical Examination/Vitals S Rheumatoid Arthritis History wevents experienced during previous intolerance, side effects) *dose (Disease Assessment will be a Laboratory Tests include CBC titer, FBG, HBsAg and HCV-Ab. Stanford University-Health As Poor prognostic factors: Press 	igns: Height will be vill include RA Dura ous treatment and lifthe patient receiv lone by Clinical Dis C, ESR assessed by sessment Question ence of 1 or more o	collected in V1 d tion, Previous/C Reason for startii ed loading dose ease Activity Ind v Westergren me naire (HAQ Disa f; Bony erosions	only. urrent therapies i ng Leflunomide* or not) and Previ ex (CDAI). thod (First hour), bility Index). by radiograph, H	ncluding duration, (previous DMARE ous X-RAY report C-reactive protein igh swollen joint c	dose, adverse even Is failure, insufficient s. n (titer), AST, ALT, S nount, Extra-articular	ts/serious adverse response, allergy r Cr, Sr ACPA, Sr disease (nodules,	

High acute phase reactants (CRP and ESR) or High RF and/or anti-CCP.

4. Study and Disease Information

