6.3.2. Selection of Investigators

The study will be conducted by rheumatologists.

In order to ensure the representativeness of investigators, the participating investigators will be randomly selected among an extended list of sites (private clinics; rheumatologist) provided by the study sponsor.

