8.7.2. Comparative Analysis

o Student t-test and One Way ANOVA to estimate the comparison between the treatment

Study Protocol: EVA_CLEAR_11022017 Version Number

arms for the numerical variables (according to their distribution; non-parametric substitution tests could be used).

- Paired t-test and repeated measure ANOVA test to estimate the change in numerical variables throughout the study visits (according to their distribution; non-parametric substitution tests could be used).
- Chi2 test (or Fisher's Exact test) for unpaired and McNemar's test for paired categorical variables.
- All tests will be performed on the 5% level of significance.
- Any deviation(s) from the original statistical plan will be described in the final report.

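### Patients are nested in 24 randomly selected clinics, but neither the sample size nor the primary within-patient analysis allows for clustering by clinic

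*Combined protocol and SAP*

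**What the plan says.** The Synopsis (Section 3) gives the expected number of sites as "24 sites (Private clinics") and about 17 patients per site, 400 in all. Under Section 6.3.2 the investigators are "randomly selected among an extended list of sites (private clinics; rheumatologist) provided by the study sponsor", with representativeness as the stated aim.

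The sample size text (Section 8.1, repeated in the Synopsis) reads "Considering an alpha error of 5% using two-sided 95% CI of Wilcoxon signed-rank test and a study power of 80"%, and concludes that "a sample of 332 patients will be required to detect an effect size of 0.158 between baseline and study endpoint". It then adds 20% for drop-out: "Thus, a sample of 398 patients will be appropriate that rounded to 400 patients". No ICC, design effect or number of sites enters the calculation.

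For the primary change from baseline, Section 8.7.2 lists "Paired t-test and repeated measure ANOVA test to estimate the change in numerical variables throughout the study visits", with non-parametric substitutes where needed and every test at the 5% level. Site is not among the covariates in Section 8.6. No random site effect, stratification by site or cluster-robust variance appears anywhere. Section 8.8 leaves missing, unused and spurious data to a SAP but does not send site effects there.

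**The concern.** Clinics are the sampling unit and patients come in groups within them. Leflunomide is prescribed at the treating physician's sole decision (Sections 6.3.1.1 and 9.1), treatment is not randomised, and no central CDAI assessor is named. Mean change may therefore differ from clinic to clinic. If it does, patients of one clinic carry partly the same information, and a paired t-test or signed-rank test that counts each of them as independent understates the standard error.

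This matters because the main product of a single-arm study is an estimated change with its interval. Intervals that are too narrow overstate what 24 clinics can say about Egyptian practice, and the nominal 5% level and stated 80% power both rest on an unstated assumption that the ICC is zero.

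**Working it through.** **The plan's own figure.** Inputs from Section 8.1: two-sided 5%, 80% power, effect size 0.158, Wilcoxon signed-rank test.

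- Paired z formula: ((1.960 + 0.842)/0.158)² = 314.4.
- Divided by the signed-rank efficiency for normal data, 3/π = 0.955: 329.2.
- Noncentral t on n × 3/π instead of the normal: n = 332, power 80.1%. This matches the stated 332, with no clustering term.
- 332 × 1.2 = 398.4 matches the stated 398.

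**Inputs for the check.** There are 24 clinics. The number analysed, N, lies between 320 (400 × 0.8, if drop-outs contribute nothing) and 400 (if last observation carried forward under Section 8.3 keeps everyone). Clinics are taken as equal in size, so m = N/24 is 13.3 to 16.7. The ICC of the change score, ρ, is an assumption with range 0.01 to 0.10.

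**Formulas.**

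- Design effect: DE = 1 + (m − 1)ρ.
- True size of the unadjusted 5% test: 2[1 − Φ(1.96/√DE)].
- Ratio of correct to unadjusted interval width: √DE.
- Power of a site-adjusted test held at 5%: noncentral t, as above, with N replaced by N/DE.
- Power of the planned unadjusted test: Φ((δ − 1.96)/√DE) plus a negligible opposite tail, with δ = 0.158 × √(N × 3/π).

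**One case in full** (N = 320, ρ = 0.05). DE = 1 + 12.33 × 0.05 = 1.617, and √DE = 1.27. Size = 2[1 − Φ(1.96/1.27)] = 12.3%. Effective N = 320/1.617 = 198, giving adjusted power of 58%. δ = 0.158 × √305.6 = 2.76, so unadjusted power = Φ((2.76 − 1.96)/1.27) = 74%.

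**Results** (first value N = 320, second N = 400):

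| Assumed ICC | DE | True size, unadjusted | Width ratio | Power, site-adjusted at 5% | Power, unadjusted |
|---|---|---|---|---|---|
| 0 | 1.00 / 1.00 | 5.0% / 5.0% | 1.00 / 1.00 | 79% / 87% | 79% / 87% |
| 0.01 | 1.12 / 1.16 | 6.4% / 6.8% | 1.06 / 1.08 | 74% / 82% | 78% / 85% |
| 0.02 | 1.25 / 1.31 | 7.9% / 8.7% | 1.12 / 1.15 | 69% / 77% | 76% / 84% |
| 0.05 | 1.62 / 1.78 | 12.3% / 14.2% | 1.27 / 1.34 | 58% / 63% | 74% / 80% |
| 0.10 | 2.23 / 2.57 | 19.0% / 22.1% | 1.49 / 1.60 | 45% / 48% | 70% / 76% |

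**Simulation** (3000 runs, 332 patients in 24 clinics). The ordinary signed-rank test rejected a true null in 6.4%, 8.2%, 11.3% and 19.4% of runs at ICC 0.01, 0.02, 0.05 and 0.10 (5.7% at ICC 0, within simulation error). A t-test on clinic means with 23 degrees of freedom stayed at 4.8% to 5.5%.

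**Between-group t-tests** (simulated, 336 patients). With groups split by clinic, type I error was 13.5% and 20.5% at ICC 0.05 and 0.10. With groups balanced within clinics it was 4.5% and 3.7%.

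**The case against.** The strongest reply is that the documents contain no ICC. At ICC 0 the method itself costs nothing, and at 0.01 the size is only 6.4% to 6.8%. Stable differences between clinics in baseline level cancel in an absolute change, Section 13.1 promises uniform assessment standards, the HAQ-DI is completed by patients, and no passage says that the treating rheumatologist scores the CDAI. This stands, and it makes the finding conditional. It does not remove it: uniform standards do not show that the ICC is zero, and Section 8.4.1 specifies relative change and CDAI severity categories, in which differences in level do not simply cancel.

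Three stronger readings are tempting, and the documents do not support them:

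- **The planned test's power falls to 45%.** That figure belongs to a site-adjusted test held at 5%. The planned unadjusted test keeps power of 70% to 85% over the same range, partly because its error rate is inflated.
- **Any ICC pushes power below 80%.** With 400 analysed, the site-adjusted test still has about 82% at ICC 0.01 (78.5% with 23 degrees of freedom). With 320, power is 78.6% before any clustering. That part of the gap comes from the drop-out arithmetic, a separate matter.
- **Every planned test is too liberal.** For the between-group comparisons in Section 8.7.2 the direction depends on how groups fall across clinics, which the documents do not say.

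The power loss also applies only at the planning effect. At an assumed true effect of 0.3 with 332 patients, an adjusted test with 23 degrees of freedom still has 98% power at ICC 0.05 and 92% at 0.10. Interval width is then the main harm.

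**Conclusion.** The point holds in conditional form, for the primary within-patient changes in CDAI and HAQ-DI. Section 8.1 assumes independent patients, the design samples clinics, and Section 8.7.2 does nothing to bridge the two. Any positive ICC of the change makes the planned intervals too narrow and the true error rate higher than 5%. The harm is small at ICC 0.01 and substantial at 0.05 and above, where the true size is at least about 12% and correct intervals are at least 1.27 times as wide.

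These sizes rest on the assumed ICC range, equal clinic sizes, approximate normality and 320 to 400 patients analysed. A reader might infer that the 5% and 80% certainly fail; without an ICC in the documents that cannot be said. No size is claimed for the descriptive intervals in Section 8.4.2, since an ICC range for change does not carry over to them.

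**What to change.** In Section 8.7.2, analyse the primary change in CDAI and HAQ-DI with a linear mixed model that has a random site intercept, or with cluster-robust standard errors and a small-sample correction for 24 clusters. Report the primary confidence intervals from that analysis. Neither option needs the ICC in advance, because the data supply the clustering.

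In Section 8.1, state that the 80% power assumes an ICC of 0, and give the power of the site-adjusted test over a stated ICC range.

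The cost is SAP wording, slightly wider intervals and a less favourable stated power. No extra patients or data are needed, since each patient's site is known. The change restores valid intervals; it does not restore 80% power at effect size 0.158 if the ICC is appreciable. Fixing it in advance also avoids a choice between two standard errors after the results are seen.

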8.1. Determination of Sample Size

The primary objective of CLEAR study is to assess the clinical efficacy of Leflunomide as first line therapy and as add-on therapy to other DMARDs (such as Methotrexate, Hydroxychloroquine, Sulfasalazine) with or without Steroids as measured by the mean relative change in Clinical Disease Activity Index (CDAI) and Health Assessment Questionnaire (HAQ Disability Index) among patients with active rheumatoid arthritis.

Considering an alpha error of **5%** using two-sided 95% CI of Wilcoxon signed-rank test and a study power of **80%**, a sample of **332 patients** will be required to detect an effect size of **0.158** between baseline and study endpoint, plus an expected **drop-out rate of 20%** during the 9 months observational study duration. Thus, a sample of **398 patients** will be appropriate that rounded to **400 patients**.

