8.3. Analysis Population

The obtained clinical data will be analyzed on an intention-to-treat basis. Primary analysis will be done by intention-to-treat including all eligible enrolled patients with at least one treatment dose and post first assessment score (CDAI and HAQ) attending any post treatment visit and efficacy variables will be analyzed using the last-observation-carried-forward convention (LOCF).

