11.5. Discontinuation / Withdrawal of participants from study

Each participant has the right to withdraw from the study at any time. In addition, the investigator may discontinue a participant from the study at any time if the investigator considers it necessary for any reason including:

- 1. Ineligibility (either arising during the study or retrospective having been overlooked at screening)
- 2. Significant protocol deviation
- 3. Significant non-compliance with treatment regimen or study requirements
- 4. Disease progression which requires discontinuation of the study medication or results in inability to continue to comply with study procedures.
- 5. Consent withdrawn.
- 6. Lost to follow up

The reason for withdrawal will be recorded in the CRF.

If the participant is withdrawn due to an adverse event, the investigator will arrange for follow-up visits or telephone calls until the adverse event has resolved or stabilized. Patients who withdraw from the study will not be replaced.

12. Quality Control and Quality Assurance

- 12.1. Quality Control
 - 12.1.1. In Process Quality Control of Biometrics

As per DataClin CRO SOPs, quality control by an independent qualified reviewer is performed on all biometrics related documents developed internally. This includes study protocol, case report form, informed consent form and study plans. In addition to these documents, database QC is performed automatically (programmed edit checks) and manually (manual review of line listings) to ensure that data is complete and consistent.

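### The 20% drop-out allowance is calculated as 332 × 1.2 = 398 instead of 332 / 0.8 = 415, so 400 enrolled leave 320 week-36 completers, not 332, if drop-outs are lost

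*Combined protocol and SAP*

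**What the plan says.** The same derivation appears in the synopsis (section 3, sample size justification) and in section 8.1. The test basis is given as "using two-sided 95% CI of Wilcoxon signed-rank test" with 5% alpha and 80% power, and on that basis "a sample of 332 patients will be required to detect an effect size of 0.158 between baseline and study endpoint". An expected drop-out rate of 20% over the nine months is then added, and the paragraph ends: "Thus, a sample of 398 patients will be appropriate that rounded to 400 patients". No inflation formula is given.

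Two other sections bear on what 400 enrolled will yield:

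- Section 11.5: "Patients who withdraw from the study will not be replaced".
- Section 8.3 defines the primary analysis set as "all eligible enrolled patients with at least one treatment dose and post first assessment score (CDAI and HAQ) attending any post treatment visit", with last observation carried forward (LOCF) for the efficacy variables.

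**The concern.** The 20% appears to have been applied to the wrong base. If 20% of enrolled patients drop out, the number remaining is 0.8 times the number enrolled, so the required number must be divided by 0.8. Multiplying it by 1.2 gives too few.

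At stake is whether the plan delivers the 332 patients, and the 80% power, that its own sizing paragraph sets out to protect. As there is no replacement, nothing later in the plan makes up a shortfall. The primary endpoints in section 8.4.1 run from baseline to week 36, so the number of patients actually observed at week 36 ought to be stated correctly, even though the analysis uses LOCF.

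**Working it through.** **Inputs.** From the synopsis and 8.1: two-sided alpha 0.05, Wilcoxon signed-rank test, power 80%, effect size d = 0.158, required n = 332, drop-out 20%, enrolment 398 rounded to 400. From 11.5: no replacement. From 8.3: any-visit population with LOCF.

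**1. Reproducing the 332.** Take the paired-t power function with effective sample size n × 3/π, the asymptotic relative efficiency of the Wilcoxon test for normally distributed changes. The non-centrality is d × √(3n/π).

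- n = 331: power 0.7997
- n = 332: effective n = 317.0, non-centrality 0.158 × √317.0 = 2.813, power 0.8009

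So 332 is the smallest n reaching 80% on the stated basis. It reproduces exactly and has no slack.

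**2. Reproducing the 398.** 332 × 1.2 = 398.4, the stated 398. The allowance is 20% of 332.

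**3. The enrolment that leaves 332 after a 20% loss.** N × (1 − 0.20) = 332, so N = 332 / 0.8 = 415. The plan is short by 415 − 398 = 17 patients before rounding and 415 − 400 = 15 after it, about 4%.

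**4. What 400 delivers if drop-outs are lost.**

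- Completers: 400 × 0.8 = 320, which is 12 below 332.
- Wilcoxon power at n = 320, d = 0.158: 78.6%.
- Effect size giving 80% power at n = 320: 0.161.
- Drop-out that still leaves 332: 1 − 332/400 = 17.0%.

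**5. What 400 delivers under section 8.3.** Drop-outs expected: 400 × 0.2 = 80. The analysed set reaches 332 if 332 − 320 = 12 of them have a post-baseline CDAI and HAQ. Equivalently, at most 80 − 12 = 68 of 400 (17.0%) may have none. The documents do not give this proportion, so a range is shown:

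| Drop-outs with a post-baseline score | Analysed n | Wilcoxon power at 0.158 |
|---|---|---|
| 0 of 80 | 320 | 78.6% |
| 12 of 80 | 332 | 80.1% |
| 20 of 80 | 340 | 81.0% |
| 40 of 80 | 360 | 83.2% |
| 80 of 80 | 400 | 86.9% |

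The table assumes that the standardised effect stays at 0.158 when carried-forward values are included.

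**6. Sensitivity to the test.** With a paired t-test instead (efficiency 1), the smallest n is 317 (power 0.8008), and 320 gives 80.5%.

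**The case against.** The strongest objection is that 320 is not the size of any analysis set in the plan. Section 8.3 defines only the any-visit population with LOCF. CDAI and HAQ are scheduled at week 6 and at four later visits, so for the analysed number to fall below 332, more than 68 of the 80 expected drop-outs would need to leave without a post-treatment score. This stands as a limit on the consequence: the primary analysis may well exceed 332. It does not rescue the derivation. If the 20% means patients lost to analysis, the enrolment figure is 415. If 332 means the LOCF population, overall drop-out is the wrong quantity to inflate by, and the relevant one (patients with no post-baseline score) is not given. On neither reading does a 20% rate among those enrolled lead from 332 to 398.

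A related caution also stands. Section 9.2 says improvement usually starts after 4 to 6 weeks and may continue up to 4 to 6 months. Scores carried forward from early visits may therefore show less change, and the power figures above 332 may be optimistic.

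Secondly, section 8.7.2 names the paired t-test first, with non-parametric tests as substitutes, and under it 320 is enough. That is correct, but the plan sizes on the Wilcoxon test and leaves the choice to the distribution of the data, so the written justification has to hold on the Wilcoxon basis.

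Thirdly, 24 sites at around 17 patients gives 24 × 17 = 408. The stated total is 400, and 408 × 0.8 is still only 326, with power of 79.4%.

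**Conclusion.** The concern holds and is minor. The sizing text in the synopsis and 8.1 does not deliver its own 332: the correct inflation gives 415, against 398 or 400 stated. Among week-36 completers the cost is about 1.5 points of power (80.1% to 78.6%), or a detectable effect of 0.161 in place of 0.158.

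This rests on three conditions: the 20% is a proportion of those enrolled (the ordinary meaning of a drop-out rate), drop-outs are lost, and the Wilcoxon test is the basis. The first two are readings of a paragraph that gives no formula and names no population. For the section 8.3 population, 320 is only the floor set by the 20% drop-out. The finding is therefore an error in the stated justification and does not show that the primary analysis is underpowered.

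**What to change.** Leave enrolment at 400 and replace the step from 332 to 398, in both the synopsis and 8.1, with one of these statements:

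1. 400 enrolled with 20% drop-out gives 320 week-36 completers, with Wilcoxon power of 78.6% for an effect size of 0.158 (80% for 0.161).
2. 400 enrolled gives 332 week-36 completers and 80% power provided drop-out is at most 17%. Keep the expected 20% beside it so that the gap is visible.
3. The 332 refers to the section 8.3 any-visit/LOCF population, and 400 is enough if at most 17% of those enrolled (68 patients) have no post-baseline CDAI and HAQ. State the proportion assumed, and that the effect size is taken as unchanged by carrying values forward.

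Label (1) and (2) as completer figures so that they do not conflict with 8.3. If the sponsor wishes to keep both 332 completers and 20% drop-out, the enrolment figure is 415.

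The cost of (1) to (3) is wording in two places. Either the stated power or tolerated drop-out becomes slightly less favourable, or an assumption about early drop-out has to be written down.
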